## 7.2.8. Limitations

[figure not shown]
There are several limitations to this POC study;

- POC1.2 is affected by the lack of chart validation of the events.
- Results might differ between databases because of differences introduced by the provenance of the data (hospital discharge vs. primary care).
- POC1.2 is perceived as a first step towards near real-time monitoring of vaccines in Europe, using simple visualizations only. More advanced monitoring methods (such as CUSUM or max-SPRT [5]) are not considered for reasons of simplicity.

- 
- The duration of the actual near real-time monitoring will be a maximum of 3 months aiming for at least 3 data refreshes to meet report deliverables by assigned deadlines. However, this might be too short for comprehensive system testing.

### 7.2.9. Data Management

Processing of data from the different databases will be according to ADVANCE principles (ADVANCE sharepoint: WP5 deliverables D5.1 and D5.2), with the exception that an additional data processing and storage step is foreseen to operationalize the web-application with the interactive dashboard. A graphical representation is given in Figure 1 and the different data management steps are explained below.

**Figure 2: POC1.2 data management flow**

#### 7.2.9.1. Phase 1: Extraction & transformation of local data\*

This entails the extraction of study specific individual-level data from the original databases into study specific common data model input files (CDM). This will be done locally by the database custodians. POC1.2 will use the same CDM input files as POC1, with the exception that the study period will be different and some events will be excluded (such as the pertussis complications). The CDM files will stay locally and will have the same structure across all databases.

The following three CDM input files will be created (see also [Appendix 2](#)):

- 1. Patients.txt:** This input file will contain the information of all persons recorded in the study cohort, including start and end of follow-up, date of birth, sex and the unique, encrypted person identifier.

---

 <https://publication.wiv-isp.be/workspaces/advance/wp5/Shared%20Documents/Forms/AllItems.aspx>

- 
- 2. *Vaccinations.txt:*** This input file will contain information on acellular pertussis vaccinations including date of vaccine supply/prescription, type of vaccine (coded by ADVANCE dictionary), the recorded dose and/or derived dose and the unique, encrypted person identifier.
  - 3. *Events.txt:*** This input file contains information about the date and type of the events of interest (hypotonic hypo-responsive episodes (HHE), febrile convulsions (FCONVULS), fever (FEVER), injection site reactions (ISR), somnolence (SOMNOL) and persistent crying (PCRYING) and pertussis (PERT)) and the unique, encrypted person identifier.

### **7.2.9.2. Phase 2: Transformation of CDM data files into analytical datasets\***

The study specific CDM data will be transformed and minimized into aggregated datasets suitable for further sharing and analysis. The analytical dataset will contain anonymized data only. The data transformation files will be programmed in R.

The POC1.2 programs for transforming the CDM data into the analytical datasets will be created by modifying the existing R data transformation programs created for the POC1 risk study. Cleaning of the vaccination files will follow the specifications reported in POC1 (ADVANCE sharepoint: WP5 D5.6).

Once the codes have been tested, they will be shared with the local database teams, who will run these programs locally, and ensure all needed documentations (log files, recording of site-specific changes to the code, and all versions of the code if there are modifications) are saved and archived.

### **7.2.9.3. Phase 3: Web-application server**

The data tables with summary statistics will be transferred by the data access providers to a “Shiny” server application on a password protected server controlled by P95 via secure file transfer protocol. On this server, a “Shiny” web application will transform the data tables – based on the user input- to the information to be plotted for the visual monitoring of vaccination coverage, benefits and risks. The additional data transformations on the Shiny server will allow the dashboard to be interactive.

The resulting visualizations will be accessible through a web page, with password protection and logging of user names.

---

 <https://publication.wiv-isp.be/workspaces/advance/wp5/POC%20I%20Pertussis%20study%20working%20documents/Forms/AllItems.aspx>

---

## **7.2.10. Quality Control**

### **7.2.10.1. Record Retention\***

Documents that individually and collectively permit evaluation of the conduct of a study and the quality of the data produced will be retained for a period of 5 years in accordance with Good Participatory Practice (GPP) guidelines. These documents could be retained for a longer period, however, if required by the applicable regulatory requirements or by an agreement between study partners. It will be the responsibility of the principal investigator to inform the other investigators/institutions as to when these documents no longer need to be retained.

Study records or documents may also include the analysis files, syntaxes (usually stored at the site of the database), and questionnaires.

## **7.3. Use of the data generated in this study**

The data generated in this study will be transferred to a web-based interactive dashboard, designed to facilitate the near real-time monitoring of vaccination coverage, benefits and risks. Data will only be used for the purposes of the POC1.2

## **8. PROTECTION OF HUMAN SUBJECTS**

### **8.1. Regulatory and Ethical Compliance\***

This protocol will be conducted following the ADVANCE code of conduct [6].

The European legislation describes the obligations to be fulfilled by marketing authorization holders (MAHs) and national competent authorities for medicinal products (including vaccines) authorized in the European

---

Union (EU). The European legislation does not apply to post-authorization studies conducted by organizations such as academia, medical research charities or research organizations in the public sector. These organizations should follow local requirements defined in the national legislation applicable in the countries where the research is conducted. In the context of the ADVANCE consortium, the proof-of-concept studies (POCs) will be conducted to test new approaches (data sources, methods) using a test case; within this framework, the POC studies will collect and use data on vaccines authorized in the EU. Vaccine MAHs are partners of the ADVANCE consortium and participate in the design, conduct and funding (through in-kind contribution) of the POCs concerning vaccines (at the product or substance level) for which they hold an authorization. They should therefore be considered as having input on the design of POCs, in which case requirements of the GVP applies. (21) The GVP requirements' will be addressed in the following ways:

- 1) The study protocol and study report will be posted on the EU PAS register.
- 2) The POC studies will be monitored by MAHs as PAS.
- 3) This proof-of-concept study aims to test components of the ADVANCE system for the benefit-risk monitoring of vaccines in Europe, more specifically:
  - to evaluate participating databases on ability to provide data suited for near real-time monitoring of vaccination coverage, benefits and risks
  - to test the methodology of near real-time monitoring of vaccination coverage, benefits and risks, facilitated through the development of a web-used interactive dashboard

The objectives of this study are on methodological aspects of the monitoring system and not intended to provide any information on the safety of the concerned pertussis-containing vaccines. Therefore, this study is not considered as a PASS.

#### 4) Management and reporting of adverse events/adverse reactions:

This study is observational, based on secondary use of data in large healthcare databases and will provide only incidence rates of events by vaccines type (aP). Thus, the reporting of suspected adverse reactions in the form of individual case safety reports (ICSRs) is not required and no individual adverse events/reactions will be summarized in the final study report.

ADVANCE is following the ADVANCE CoC, which differs from the ENCePP Code of conduct regarding involvement of study team members who are employed by organizations with a financial interest in one of the outcomes of the study. This specific study is about system testing using pertussis vaccines as an

---

example and has personnel from vaccine manufacturers as study team members and is compliant with ADVANCE CoC. The coverage, risk and risk-benefit parts of this study are also fully compliant with the ENCePP CoC because all the PIs of these parts are from ENCePP Inventory of Research Centres.

## **8.2. Informed Consent\***

No informed consent is necessary as this is a retrospective study using de-identified/anonymized data for secondary purposes.

## **8.3. Responsibilities of the Investigator and IRB/IEC/REB\***

The protocol and waiver of informed consent will be reviewed and approved by a properly constituted institutional review board/independent ethics committee/research ethics board (IRB/IEC/REB) before study start. A signed and dated statement that the protocol has been approved by the IRB/IEC/REB and waiver of informed consent will be given to the principal investigator before study initiation.

## **8.4. Protocol Adherence\***

Investigators will apply due diligence to avoid protocol deviations. If the investigator feels a change to the protocol would improve the conduct of the study this will be considered a protocol amendment and, unless such an amendment is agreed upon by all partners involved and approved by the IRB/IEC/REB, it will not be implemented. All significant protocol deviations will be recorded and reported in the Study Report. Specifically, reportable Protocol Deviations are those which directly or indirectly have a significant impact on any 1 or more of the following:

1. Subject's rights, safety, or well-being
2. Data integrity, i.e. completeness, accuracy, and reliability of safety, efficacy, and immunogenicity outcomes of the clinical study, and
3. Regulatory compliance.

## **9. MANAGEMENT AND REPORTING OF ADVERSE EVENTS/ ADVERSE REACTIONS**

N/A

---

## **10. PLANS FOR DISSEMINATING AND COMMUNICATING RESULTS**

### **10.1. Registration in Public Database(s)\***

Principal investigator assures that the key design elements of this protocol will be posted in a publicly accessible database, where applicable and in compliance with current recommendations.

Principal investigator also assures that key results of this study will be posted in a publicly accessible database within the required time-frame from completion of the data collection, where applicable and in compliance with current recommendations.

### **10.2. Publications\***

Further to legislated data disclosure, the results of this study will be published as a scientific paper in a peer-reviewed journal. Such a manuscript will be prepared independently by the investigators and in accordance with the current guidelines of STrengthening the Reporting of OBservational studies in Epidemiology (STROBE) and properly reported to improve reproducibility and facilitate validity assessment of healthcare database studies [7]. The ADVANCE Steering Committee will be entitled to view the results and interpretations included in the manuscript and provide comments prior to submission of the manuscript for publication

## **11. DISCLAIMER**

The study described in this protocol is conducted as part of the IMI ADVANCE project with the aim to test methodological aspects of the design, conduct and reporting of studies for vaccine benefit-risk monitoring activities. The protocol presented herein relates solely to the testing of these methodologies and is not intended to inform regulatory or clinical decisions on the benefits and risks of the exposures under investigation. Therefore any use of information from these studies should carry over this warning and be used accordingly..

---

### 13. APPENDIX 1: QUALITY ASSESSMENT

**Table: Assessment sheet for the quality /feasibility of the database to participate in the POC studies**

Quality of information				
META-DATA				
Category	Data	Measure(s)		Origin of information
Provenance of information	Sources for diagnoses (as codes or text) 
 
• primary care
 
• outpatient specialist
 
• hospital discharge
 
• emergency admission
 
• causes of death
 
	per type yes/no	Certain missingness?	Data provenance questionnaire to databases
	Vaccinations 
 
• routine childhood
 
• HPV
 
• travel
 
• influenza
 
• voluntary
 
 Drugs 
 
• prescribed/dispensed primary by GP
 
• prescribed/dispensed by specialist
 
• prescribed/dispensed during hospitalization
 
	per type yes/no	Certain missingness?	AIRR survey
	Diagnostic tests 
 
• primary care
 
• outpatient specialist
 
• during hospitalization
 
	yes/no	Certain missingness? Results?	AIRR survey
POPULATION				
Size	Number of lives (at any point in time) in population	N		Population fingerprint
	Number of subjects active at 1/1/2015	N		Population fingerprint
Dates	Missing Birthdate (no valid date entry (to be supplied by database owner))	N	Percentage on total number of lives	Attrition diagrams DBs
	Birth dates (day of birth independent of month)	Frequency of each day of the month of the DOB (1-31)	Percentage on total number of lives	Vaccine fingerprint (R)
Observation Time & lag time	Origin for the start of follow-up 
 
• birth (start of follow-up = birth)
 
• registration with database (start of follow-up > 1 month after date of birth)
 
	N	Percentage of total	Jerboa Event fingerprint
	Origin for the end of follow-up 
 
• death (end of follow-up = date of death in event file)
 
	N	Percentage of total	Jerboa Event fingerprint

	
 
exiting from database (end of follow-up < last data availability for practice)
 
	Median (5 th , 95 th percentile of lag time from date of delivery till last data)		
Gender/age	Population age Distribution (Overall and by sex) * at 1/1/2015 (representativeness of population)	N	Compared to national statistics (see D5.2)	Population fingerprint
Per type of vaccination				
Vaccinations: BCG, DTaP, DTwP, polio, Hib, HPV, Seasonal Influenza	Granularity of vaccine exposure data 
 
vaccine type
 
ATC code
 
brand
 
	N	Percent of total (vaccinetype) for these levels	Vaccine fingerprint
	Recorded dose vs. Derived dose vs. sequence (all possible combinations)	Cross-tabulation		Vaccine fingerprint, R
	Vaccination records without dose	N		Vaccine fingerprint, R
	Coverage in birth cohorts at age ....	Estimated Coverage (per methodology as developed in ADVANCE)	Comparison against WHO data, VENICE and local information	Vaccine fingerprint, R
	Coverage by dose	histogram of doses		Vaccine fingerprint, R
Per database and event				
Events	Name of event			
	Availability of codes	List of available codes per data domain	Frequency of each code in input files	Event fingerprint, Jerboa
	List of components	Name and description of query		Event team
	Frequency of events as detected by each component algorithm	Table of frequency of possible combinations		Algorithm comparison module of Jerboa
	Frequency of event as detected according to chosen algorithm(s)	Frequency by year		Component analysis
	Chosen algorithm and reason			Component analysis
Validity	PPV of chosen algorithm(s)	%	confidence measure	Output of the validity workflow
	Sensitivity of chosen algorithm(s)	%	confidence measure	Output of the validity workflow
	Specificity of chosen algorithm(s)	%	confidence measure	Output of the validity workflow
	Procedure to obtain the above estimates			Output of the validity workflow
External benchmarks	Validation Studies	Summaries of previously conducted validation		Event team & database experience

		studies in the database		
	Estimates of frequency of the event in the population represented by the database according to external data sources (e.g. literature)	Available estimates with source (and comments)		Event team & database experience

---

## 14. APPENDIX 2: COMMON DATA MODEL

The database partners will do study-specific extractions from their database structure and transform these data into the common data model structure (see below). Data will be formatted in the following input files and will stay local. The data format is identical for all the data-sites.

### 14.1. Patients.txt

For each patient, there is one record (in the case of patients' reentering the population either a suffixed ID number shall be used or the most relevant follow-up period shall be chosen) in the *Patients.txt* input file containing the following variables:

**Table S14.1: Patients.txt**

Name of the Variable	Description of the Variable	Format / Possible Values	Description of the Values
PatientID	Patient Identifier	any string maximum length: 32 characters	
Birthdate	Date of birth	YYYYMMDD.	
Gender	Gender	F M	Female Male
Startdate	Date from which the patient is eligible to be included in the study. This is typically the date the patient is entered into the registration system (date of registration with insurance/region, date GP started to collaborate). Run in periods should not be applied when defining StartDate	YYYYMMDD.	
Enddate	Date after which the patient is no longer eligible for inclusion in the study (e.g. end of registration with GP/database, insurance, moving out, death, last data draw down (whichever is earliest)).	YYYYMMDD.	

### 14.2. Vaccinations.txt

For each vaccination, there is one record in the *Vaccinations.txt* input file containing the following variables:

**Table S14.2: Vaccinations.txt**

Name of the Variable	Description of the Variable	Format / Possible Values	Description of the Values
PatientID	Patient Identifier	any string maximum length: 32 characters	
Date	Date of administration	YYYYMMDD.	
Brand	Product name of the vaccine	any string	

VacType	Type of vaccination	Will contain components of the vaccine separated by hyphens. The different components codes are listed in Annex 5.	Pertussis vaccines used in the POC I study will be any containing uPE (unclassifiable into acellular or whole-cell), aPE (acellular pertussis vacc) or wPE (whole-cell vacc) components.
ATC	ATC code of the vaccine	7 characters long string	May be shorter if not full ATC
DoseRecorded*	Dose received as specified in the database	P1, P2, etc. B1, B2, etc.	For priming doses For booster doses
DoseDerived*	Defined as dose per recommendation, as determined by the database custodian based on knowledge of the local immunization schedule and as documented in an analytic variable generated for the study	P1, P2, etc. B1, B2, etc.	For priming doses For booster doses

\* At least one of them is mandatory. Databases may choose which dose variable to prioritize based upon local expertise and results of the vaccination fingerprint. Both can be filled in at the same time.

### 14.3. Events.txt

This input file contains information about comorbidity and diagnostic events (events) of interest for the persons in *Patients.txt*; events with an invalid Patient ID or Date variable cannot be included.

For every event of interest for each patient in *Patients.txt* there is one record in the *Events.txt* input file containing the following variables:

**Table S14.3: Events.txt**

Name of the Variable	Description of the Variable	Format / Possible Values	Description of the Values
PatientID	Patient Identifier	any string maximum length: 32 characters	
Date	Date of event	YYYYMMDD.	
Eventtype *	Type of event	PERT	PERT
		FCONVULS	FCONVULS
		FEVER	FEVER
		HHE	HHE
		PCRYING	PCRYING
		SOMNOL	SOMNOL
Code	SEE APPENDIX 3		

---

15. **APPENDIX 3: CODE LISTS OF EXPOSURE EVENTS**

ATC code	ATC name	Acellular Pertussis
J07AJ52	Pertussis, purified antigen, combinations with toxoids	aP
J07CA02	Diphtheria-pertussis-poliomyelitis-tetanus	aP
J07CA06	Diphtheria-hemophilus influenzae B-pertussis-poliomyelitis-tetanus	aP
J07CA09	Diphtheria-hemophilus influenzae B-pertussis-poliomyelitis-tetanus-hepatitis B	aP
J07AG52	Hemophilus influenzae B, combinations with pertussis and toxoids	aP
J07AJ02	Pertussis	aP
J07AJ51	Pertussis	wP
J07CA11	Diphtheria-Hemophilus influenzae B-pertussis-tetanus-hepatitis B	?
J07CA12	Diphtheria-pertussis-poliomyelitis-tetanus-hepatitis B	?
J07CA13	Diphtheria-hemophilus influenzae B-pertussis-tetanus-hepatitis B-meningococcus A + C	?

## 16. APPENDIX 4: CODE LISTS OF BENEFIT AND RISK EVENTS

Variable	Role	Data source(s)	Operational definition*
Fever	Safety outcome	Participating healthcare databases	ICD9:078.2, 780.6 ICD10: P81.9, R50 READ-CTV3: 1653. 2E34., 2EZ., A782., R006.,R0060, R0061, R0062, R0063, R006z, X76Df, X76Di, X76Dk, X76DI, X76EF,X76EI, X76EI, XM05S, XM09q, XM0yv, XM0yw, XM1AX, Xa9sd, READ-v2: 165., 165.,2E...,A782.,R006. ICPC: A03
Somnolence	Safety outcome	Participating healthcare databases	ICD-9:780.09, 780.54 ICD-10: G47.1, R40.0 READ-CTV3: R0000, R0001, R0054,X007w, X007x, XM06R, Xa2bY, XaC0p READ-v2: 1B67., 1BX1.,2234.,E2743, R0000,R0001, R0054 ICPC: none (text extractions)
Persistent crying, irritability	Safety outcome	Participating healthcare databases (except SSI/AUH)	ICD9: 780.92, 780.95 ICD10: R45.83, R68.11 READ-CTV3: 1B1I0, Xa2lv, Xa9zv READ-v2: 1B1I0 1B1P. ICPC: A15
Febrile convulsions	Safety outcome	Participating healthcare databases	ICD-9: 780.31; 780.32 ICD10: R56.0 READ-CTV3: R0030; XM03I READ-v2: 1B6B.; R0030 ICPC: none
Hypotonic hypo- responsive episode (HHE)	Safety outcome	Participating healthcare databases	ICD-9: 770.88; 782.5; 782.61; 799.02 ICD10: P84; R09.02; R23.0; R23.1 READ-CTV3: R025.; R0260; R2y01; X76qQ; XM041; XM07N; XM09U; XM09U;Xa9E7 READ-v2: R025.; R0260; R2y01 ICPC: none

Variable	Role	Data source(s)	Operational definition*
Pertussis	Benefit outcome	Participating healthcare databases	ICD-9: 033.9; 484.3 ICD-10: A37 READ-CTv3: A33y. A33yz; A33z.; Ayu39; Ayu3A; H243.; X7018; XE0Qw; XE0Qw; XM00D READ v2: A33.. Ayu39; Ayu3A; H243. ICPC: R71

\*any of the codes would qualify

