### **7.2.6.3. Outcomes, Operationalization and Validation**

#### **OUTCOMES**

The risk outcomes of interest will be the same as in POC 1. However, injection site reactions and generalized convulsions were excluded. The exclusion of injection site reactions is based on the experience of POC 1, which demonstrated that many participating databases were able to extract general skin and muscle related events, signs and symptoms that potentially were not occurring at an injection site. The absence of "injection site" related information in some databases resulted therefore in a broad spectrum of extracted skin and muscle events, signs and symptoms that have been considered to be too sensitive and not specific enough to be further included as potential adverse events of interest in the POC 1.2. Generalized convulsions have been excluded because the experience from POC 1 showed that febrile convulsions/seizures dominated the entity of the convulsions/seizures. As most of the databases provided highly specific codes for the identification of febrile convulsions/seizures, we decided to continue with febrile convulsions/seizures only. The outcomes of interest (and associated risk windows) are listed in the Table 1. The benefit outcome is confirmed or probable pertussis.

---

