#### **OPERATIONALIZATION\***

Outcome events will be obtained from the databases using diagnosis codes or free-text proxies (code lists as in POC1 listed in [Appendix 4](#)).

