### 7.2.7.5. Statistical Methods

In POC1.2, the objective is near real-time visual monitoring of vaccination coverage, benefits and risks using aP vaccination as the test case. As such, we will monitor epidemiological measures including, vaccination coverage and incidence rates as they evolve over time. The monitoring will be facilitated through the use of a “Shiny” web-application [4] with a user-friendly interactive dashboard containing three monitoring tabs for visualization of coverage, benefits and risks. This dashboard will be interactive and allow for inter-country comparisons.

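### The pertussis code list in Appendix 4 has unequal scope across coding dictionaries (category level in ICD-10 and Read v2, one 033 subcode plus 484.3 in ICD-9), which may bias the inter-country benefit comparison

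*Protocol*

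**What the plan says.** Section 7.2.6.3 of the protocol sets the outcome: "The benefit outcome is confirmed or probable pertussis". Its operationalization paragraph says how cases are found: "Outcome events will be obtained from the databases using diagnosis codes or free-text proxies", with the code lists taken over from POC1 and printed in Appendix 4.

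The pertussis row of Appendix 4 gives, by dictionary:

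- ICD-9 and ICD-10: "ICD-9: 033.9; 484.3 ICD-10: A37"
- Read CTV3: "READ-CTv3: A33y. A33yz; A33z.; Ayu39; Ayu3A; H243.; X7018; XE0Qw; XE0Qw; XM00D"
- Read v2 and ICPC: "READ v2: A33.. Ayu39; Ayu3A; H243. ICPC: R71"

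The only rule for applying the list is the footnote: "any of the codes would qualify". It does not say whether a listed code brings in the codes beneath it.

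Section 7.2.7.5 says what the curves are for: "This dashboard will be interactive and allow for inter-country comparisons". Pertussis incidence is the only measure on the benefits tab.

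**The concern.** An outcome extracted through several dictionaries is comparable between databases only if each dictionary's list covers the same clinical concept. Here the ICD-10 and Read v2 lists appear to take in a whole category, and the ICD-9 list one branch of its category.

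If so, two countries with the same disease would show different pertussis rates because of the list alone. The display would give no sign of this. The caveat on between-database differences in Section 7.2.8 mentions data provenance (hospital discharge or primary care) and not code scope.

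**Working it through.** The plan gives no figure on this point, so there is none to reproduce. The check is a comparison of the lists, followed by a sensitivity calculation.

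**1. Scope by dictionary.**

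| Dictionary | Entry in Appendix 4 | Level |
|---|---|---|
| ICD-10 | A37 | undotted category |
| Read v2 | A33.., with Ayu39, Ayu3A, H243. | parent stem plus extra codes |
| ICD-9 | 033.9; 484.3 | one subcode of 033 plus one other code; no bare 033 and no other 033 subcode |
| Read CTV3 | A33y., A33yz, A33z. and others | individual codes; no A33.. stem |
| ICPC | R71 | single code |

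The CTV3 entries show that A33 has codes beneath it.

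**2. Does a reading rule remove the difference?** If child codes are included, A37 and A33.. expand to their whole categories, while 033.9 stays one branch of 033. If matching is exact, 033.9 still misses the rest of 033, and A37 would also miss any dotted A37 record. The two readings give different mismatches, and neither gives equal scope. The fever row does not settle the rule: its CTV3 entry lists R006. together with its children, and its Read v2 entry lists R006. alone.

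**3. Which databases are affected?** Section 7.2.3 describes SIDIAP as ICD-10 and the Danish patient registry as ICD-10 after 1993. The Read rows presumably serve RCGP, whose dictionary is not stated. No dictionary is stated for ASLCR, ARS or Pedianet. Elimination leaves ICD-9 or ICPC for these three. Every outcome in Appendix 4 has ICD-9 codes, so ICD-9 use somewhere among the sites is a reasonable inference, though not a stated fact.

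**4. Size.** Let s be the share of cases in an ICD-9 database that carry only unlisted 033 subcodes and are not found by another route. Child codes are taken as included for ICD-10 and Read v2. Then:

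- displayed rate = (1 - s) × full-category rate
- apparent ratio of a full-category database to an ICD-9 database with equal disease = 1/(1 - s)

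The protocol gives no s, so these values are assumptions:

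| s | Displayed / full-category rate | Apparent ratio |
|---|---|---|
| 5% | 0.95 | 1/0.95 = 1.05 |
| 25% | 0.75 | 1/0.75 = 1.33 |
| 50% | 0.50 | 1/0.50 = 2.0 |

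**5. Against random error.** Section 7.2.7.4 gives incidence rates from 2 to 100 per 10,000 person-years and database sizes of about 37,000 and 220,000 person-years a year. It does not say which rate applies to pertussis. I take the lowest rate as an assumption, and use the two sizes for scale only. The relative 95% margin is 1.96/√(expected events):

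- 37,000 person-years: 0.0002 × 37,000 = 7.4 events a year; 1.96/√7.4 = 72%
- 220,000 person-years: 0.0002 × 220,000 = 44 events a year; 1.96/√44 = 29.5%

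Over one year at that rate, a 5% or 25% deficit lies within the margin in both databases. A 50% deficit exceeds it in the larger one only. By week the expected counts are 7.4/52 = 0.14 and 44/52 = 0.85, so random error dominates a single weekly point. The bias does not shrink as person-time accrues, whereas the margin does.

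**The case against.** The strongest case against the point has four parts.

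- **Other routes to a case.** Free-text proxies are allowed, ASLCR holds a registry of notifiable infectious diseases, and a child with both a listed and an unlisted code is still captured. This stands as a reason why s may be small. It does not repair the list: no free-text proxy for pertussis is named, and the protocol does not say that the notification registry feeds the outcome.
- **Harmonization and benchmarking.** Section 7.2.6.3 reports that codes were mapped and rates benchmarked successfully. Comparing rates between databases cannot by itself separate a narrower list from a real or provenance difference.
- **Purpose of the study.** This is a system test without hypothesis testing. No success criterion in Section 7.1 depends on the absolute pertussis rate, and a stable omission leaves trends within a database usable. All of this stands, and it limits the consequence to the comparison between countries.
- **Which scope is right.** The difference between lists does not show that the broad one is correct. A37 and A33.. could be wider than the intended outcome. This stands, and the fix allows either direction.

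A reader might infer more than the protocol supports:

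- **That the confirmed cases are the ones dropped.** The protocol prints no meaning for 033.9 or any other 033 subcode, and no dictionary row separates confirmed from probable cases.
- **That the Italian databases are under-counted.** Their dictionaries are not stated.
- **That only ICD-9 sites are affected.** The CTV3 list also lacks the parent stem, so its scope is open too.
- **That the curves cannot be compared at all.** The size of any loss is unknown.

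**Conclusion.** The pertussis definition has unequal scope across dictionaries, without explanation, and nothing else in the protocol corrects this. Any database coding in ICD-9 would miss cases recorded only under unlisted 033 subcodes, so its pertussis incidence may be too low and the inter-country display may be biased. The conclusion assumes that at least one participating database codes in ICD-9 and that A37 and A33.. are meant to include their child codes. The first is an inference and the second is not written down. The size cannot be fixed from the protocol: over assumed shares of 5% to 50%, the displayed rate runs from 0.95 to 0.50 of the full-category rate. The point is worth correcting because it concerns the sole benefit outcome and the change is small. It does not touch the feasibility, refresh or timeliness criteria.

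**What to change.** In the pertussis row of Appendix 4, give all dictionaries the same scope in one of two ways:

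- replace the ICD-9 entry with '033 (all subcodes); 484.3', to match A37 and A33..; or
- restrict every dictionary to the same set of subcodes, listed explicitly.

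Check the CTV3 list against the chosen scope. Add to the footnote that child codes of a listed code are included, and state in Section 7.2.3 which dictionary each database uses. If a narrower ICD-9 list was intended, give the reason and name the difference in Section 7.2.8. Extract the baseline from 01 January 2014 with the aligned list, so that baseline and monitoring period share one definition.

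The cost is a changed row and footnote, the amendment approval that Section 8.4 requires, and one re-extraction at the affected sites. Pertussis rates there may no longer match POC1, which used the present list; the report should say so.
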